2.5.4 Supportive analyses

In order to assess the robustness of the primary endpoint, the following analyses are planned:

- Using a non-informative prior, i.e. uniform prior Beta (0.5, 0.5), for both treatment groups
- A logistic regression model with treatment in the model. ORs along with the respective 2-sided 80% confidence interval (CI) will be derived for the treatment comparison.

Furthermore, the primary analysis will be repeated based on only signs and symptoms of GCA in order to mitigate against the possibility of biasing.

In addition, the reasons why a patient is determined to be a responder or non-responder to the primary endpoint will be summarized.

Subgroup analyses (see Section 2.2.1 for further details) will only be performed if at least 5 patients are present in each subgroup. Some grouping of classes will be considered if there are too few patients in some subgroups.

2.6 Analysis of the key secondary objective

There are no key secondary objectives in this study.

2.7 Analysis of secondary efficacy objectives

Patients will be analyzed according to the treatment assigned at the last randomization (see Section 2.2 for further details) for the FAS.

The analyses of the secondary efficacy objectives will not take into account the prior information, it is based only on information from this study.

2.7.1 Secondary endpoints

The following secondary endpoints will be analyzed:

- Proportion of GCA patients who adhere to the prednisolone taper regimen and are in sustained remission at Week 52
- Remission rate at Week 12
- Time to first GCA flare after Baseline (up to and including Week 52)
- Total cumulative prednisolone dose from start of co-administered treatment to Week 28, 52
- Proportion of patients on prednisolone dose ≤ 5 mg/day at Week 19, 28, 52
- Change from Baseline in PhGA VAS at Week 4, 8, 12, 16, 20, 24, 28, 36, 44 and 52
- Change from Baseline in PGA VAS at Week 4, 8, 12, 16, 20, 24, 28, 36, 44 and 52
- Change from Baseline in FACIT-Fatigue at Week 4, 8, 12, 16, 20, 24, 28, 36, 44 and 52
- Change from Baseline in SF-36 at Week 4, 8, 12, 16, 20, 24, 28, 36, 44 and 52
- Change from Baseline in EQ-5D at Week 4, 8, 12, 16, 20, 24, 28, 36, 44 and 52
- Change from Baseline in CRP (mg/L) at Week 4, 8, 12, 16, 20, 24, 28, 36, 40, 44, 48, 52
- Change from Baseline in ESR (mm/hr) at Week 4, 8, 12, 16, 20, 24, 28, 36, 40, 44, 48, 52

2.7.2 Statistical hypothesis, model, and method of analysis

The proportion of patients in sustained remission until Week 52 (Yes, No) will be summarized descriptively for each treatment group. Note: Sustained remission at Week 52 refers to patients without flare until Week 52 and in adherence to the protocol prednisolone taper regimen. Flare is determined by the investigator and defined as the recurrence after remission of signs or symptoms of GCA and/or ESR \geq 30 mm/hr and/or CRP \geq 10 mg/L attributable to GCA. In addition, the reasons why a patient is determined to be a responder or non-responder to patients in sustained remission until Week 52 will be summarized.

The proportion of patients in remission (Yes, No) at each time point will be summarized descriptively for each treatment group. Note: Remission refers to the absence of flare. This summary table will only summarize remission information up to 4 weeks post last administration of study treatment.

The time to first GCA flare after remission (up to and including Week 52) will be summarized using Kaplan Meier curves. Descriptive statistics will also be provided for time to first GCA flare after remission in days (up to and including Week 52). This will also include information on follow-up. Follow-up is defined as:

• (Date of event or censoring – Baseline date) + 1 (regardless of censoring)

Total cumulative prednisolone dose from the first dose of co-administered prednisolone treatment to Weeks 26, Week 28, and 52 will be summarized over time by treatment group. Note: Prednisolone dose refers to prednisolone dose taken for GCA.

The number and percentage of patients on prednisolone dose \leq 5mg/day at Week 19, 28 and 52 will be summarized by treatment group. Note:

- Prednisolone dose refers to prednisolone dose taken for GCA.
- Prednisolone dose refers to the average co-administered prednisolone treatment in the week of interest.
- Prednisolone dose for GCA will be based on the information collected on the "Dosage Administration Record-Prednisolone" eCRF. However as the prednisolone taper regimen is planned to be 26-weeks in duration, the Investigator is not required to enter daily prednisolone records on the "Dosage Administration Record-Prednisolone" eCRF post Week 26 unless the patient has taken additional prednisolone for GCA. Therefore if the patient is still in the study at the post Week 26 week of interest and has no prednisolone information in the "Dosage Administration Record-Prednisolone" eCRF for that week of interest the patient will be regarded as having 0 mg/day at that week of interest.

Descriptive summary statistics for the change as well as relative change from baseline of PhGA VAS to each study visit of interest will be presented for each treatment group. Change from baseline will only be summarized for patients with both baseline and post baseline values.

The analysis of the PRO secondary endpoints is detailed in Section 2.10.

Descriptive summary statistics for the change from baseline of CRP and ESR to each study visit of interest will be presented for each treatment group. Change from baseline will only be summarized for patients with both baseline and post baseline values. Further details are provided in Section 2.8.3. This analysis will also be presented for the following subgroups:

- Sustained remission until Week 28 (Yes, No)
- Sustained remission until Week 52 (Yes, No)

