### 9.4.2 Statistical model, hypothesis, and method of analysis

A binomial distribution will be assumed for the observed data from this study. Due to the conjugate nature of the Beta distributions, the posterior distributions for the sustained remission response rates until Week 28 for secukinumab and placebo will also be Beta distributions.

The response rate of the comparable placebo-arm of the GIACTA study (Stone et al 2017) will be used as the prior distribution for the placebo response rate for the primary endpoint in this study. The parameters of this Beta distribution are 10 and 43, i.e. Beta (10, 43). The prior distribution for the response rate on secukinumab will be a Beta distribution with parameters 1/2 and 1/2, i.e. Beta (1/2, 1/2). This prior distribution was chosen because it has low weight to reflect the lack of current knowledge on the response rate on secukinumab in GCA.

Posterior distributions for the estimate of the OR, risk-ratio (RR) and risk difference (RD) will be derived by sampling from the posterior distributions of the response rates of secukinumab and placebo. The associated median and 95% credibility interval will be presented. In addition the probability of the posterior distribution of the OR of the comparison of secukinumab versus placebo being greater than 1 will be provided.

The posterior median OR will be calculated such that the OR is in favor of secukinumab. The probability of the posterior distribution of the OR of the comparison of secukinumab versus placebo being greater than 1 will be provided.

Furthermore, the proportion of patients in sustained remission until Week 28 will be summarized descriptively by treatment group.

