### **9.5 Analysis of secondary variables**

#### **9.5.1 Efficacy variables**

The following secondary efficacy endpoints for this study will be analyzed for the FAS:

- Remission rate at Week 12
- Time to first GCA flare after remission (up to Week 52)
- Total cumulative prednisolone dose over 28 Weeks and 52 Weeks
- Proportion of GCA patients in sustained remission at Week 52
  - Definition of remission: absence of flare.
  - Definition of sustained remission: patients without flare until Week 52 and in adherence to the protocol prednisolone taper regimen + prednisolone-free phase from Week 27 onwards
  - Definition of flare: determined by the investigator and defined as the recurrence after remission of signs or symptoms of GCA and/or erythrocyte sedimentation rate (ESR)  $\geq 30$  mm/hr and/or CRP  $\geq 10$  mg/L attributable to GCA
- Proportion of patients on prednisolone dose  $\leq 5$  mg/day at Week 19, Week 28 and Week 52

- Change from Baseline PGA at Week 4, 8, 12, 16, 20, 24, 28, 36, 44 and 52
- Change from Baseline PhGA at Week 4, 8, 12, 16, 20, 24, 28, 36, 44 and 52
- Change from Baseline FACIT-Fatigue at Week 4, 8, 12, 16, 20, 24, 28, 36, 44 and 52
- Change from Baseline SF-36 at Week 4, 8, 12, 16, 20, 24, 28, 36, 44 and 52
- Change from Baseline EQ-5D at Week 4, 8, 12, 16, 20, 24, 28, 36, 44 and 52
- Change from Baseline CRP at Week 4, 8, 12, 16, 20, 24, 28, 32, 36, 40, 44, 48 and 52
- Change from Baseline ESR at Week 4, 8, 12, 16, 20, 24, 28, 32, 36, 40, 44, 48 and 52

Similar to the primary endpoint methodology, the posterior distributions for the estimate of the OR, RD, and RR will be derived by sampling from the posterior distributions of the remission response rates at Week 12 of secukinumab and placebo. The prior distribution for the remission response rates at Week 12 for both treatment groups will be a Beta distribution with parameters 1/2 and 1/2, i.e. Beta (1/2, 1/2). The associated median and 95% credibility interval will be presented. Patients that withdrew from the study or entered “escape” therapy will be classified as non-responders from the point of withdrawal/escape onwards. Patients with a missing remission status at a particular time point will be classified as non-responders at that time point. In addition, the proportion of patients in remission over time will be summarized descriptively by visit and by treatment group.

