The time to first GCA flare after remission (up to Week 52) will be summarized using Kaplan Meier curves. Patients who:

- Withdraw from the study prior to Week 52 will be censored at the time of withdrawal
- Do not have a flare up to Week 52 will be censored at Week 52

Descriptive statistics will also be provided for time to first GCA flare after clinical remission (up to Week 52).

Total cumulative prednisolone dose over 28 and 52 weeks will be summarized over time by treatment group.

The proportion of GCA patients in sustained remission at Week 52 will be analyzed using the methods outlined in Section 9.4.2. Patients who (1) do not achieve remission within 12 weeks of Baseline; or (2) are in the “escape arm”; or (3) drop out from the study prior to/on Week 52, or (4) do not have information to evaluate sustained remission response at Week 52, will be classified as non responders. Patients receiving less than the full amount of prednisolone as required by the taper, e.g. due to missing tablets, will not be classified as non-responders.

The number (and percentage) of patients on prednisolone dose  $\leq$ 5mg/day at Week 19, 28 and 52 will be summarized by treatment group.

The continuous secondary efficacy endpoints (actual value and change from baseline value) will be summarized descriptively by visit (where applicable) and by treatment group.

For SF-36, the following variables will be evaluated:

- SF-36 domain scores

- SF-36 domain score responders
  - Type I responders (improvement of  $\geq 5$  points in  $\geq 6$  domains)
  - Type II responders (improvement of  $\geq 10$  points in  $\geq 3$  domains)
- SF-36 PCS and MCS scores
- SF-36 PCS and MCS score responders
  - Type I responders (improvement of  $\geq 2.5$  points)
  - Type II responders (improvement of  $\geq 5$  points)

The EQ-5D is a questionnaire with 5 questions (regarding mobility, self-care, usual activities, pain/discomfort, and anxiety/depression) each with three categories (no problem, moderate problem, severe problems) and a health state assessment from 0 (worst possible health state) to 100 (best possible health state) (see [Section 6.5.2.1.4](#) for further details). The number and percentage of subjects in each of the three categories for each question will be presented by visit and treatment group. Summary statistics will be provided for the health state assessment by visit and treatment group.

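### SAP 2.7.2 replaces the protocol's Bayesian between-arm comparisons of Week 12 remission and Week 52 sustained remission with per-arm percentages, without declaring the change

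*SAP*

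**What the plan says.** **Protocol, Week 12.** Section 9.5.1 states: "Similar to the primary endpoint methodology, the posterior distributions for the estimate of the OR, RD, and RR will be derived". It asks for the median and 95% credibility interval. It also fixes the prior: "The prior distribution for the remission response rates at Week 12 for both treatment groups will be a Beta distribution", with both parameters 1/2. A descriptive summary of remission by visit is requested on top of this comparison.

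**Protocol, Week 52.** Section 9.5.1 states: "The proportion of GCA patients in sustained remission at Week 52 will be analyzed using the methods outlined in Section 9.4.2". Section 9.4.2 requires posterior OR, RR and RD with median and 95% credibility interval, and adds that "the probability of the posterior distribution of the OR of the comparison of secukinumab versus placebo being greater than 1 will be provided". Its priors are Beta(10, 43) for placebo and Beta(1/2, 1/2) for secukinumab.

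**SAP.** Section 2.7.2 gives for Week 52: "The proportion of patients in sustained remission until Week 52 (Yes, No) will be summarized descriptively for each treatment group". For remission by visit, which includes Week 12, it gives: "The proportion of patients in remission (Yes, No) at each time point will be summarized descriptively for each treatment group". Section 2.7 opens with: "The analyses of the secondary efficacy objectives will not take into account the prior information". Section 4 lists three changes from the protocol: the cut-point of the baseline prednisolone subgroup, removal of redundant adherence wording, and a time origin changed from clinical remission to Baseline. None of them concerns the method for these two endpoints.

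**The concern.** The protocol separates these two endpoints from the secondary endpoints it only summarizes, such as the proportion on prednisolone 5 mg/day or less and the continuous measures. For those others the SAP follows the protocol, and they are not at issue. For these two, a planned treatment comparison has disappeared.

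The secondary objective in Protocol Table 2-1 is efficacy versus placebo, and SAP Section 1 says the study report is meant to support a Phase III program. Two percentages side by side do not show how precisely the difference is known with about 25 patients per arm. A reader can form a difference and an interval from the published counts, but that would not be the planned comparison. At Week 52 the answer also depends on which placebo prior is used, and that choice should not be made once results are known.

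**Working it through.** The documents give no figure to reproduce here. The check compares the texts and then illustrates what is lost.

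**Step 1: set the texts side by side.**

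| Endpoint | Protocol 9.5.1 | SAP 2.7.2 |
|---|---|---|
| Remission, Week 12 | Posterior OR, RD, RR; median and 95% interval; Beta(1/2, 1/2) in both arms; descriptive summary in addition | Proportion per arm |
| Sustained remission, Week 52 | Method of 9.4.2: posterior OR, RD, RR; median and 95% interval; P(OR > 1) | Proportion per arm |

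**Step 2: look for the comparison elsewhere in the SAP.** Section 2.7.3 contains only non-responder and censoring rules. In Section 5.5 the Bayesian code stands under the primary analysis. A logistic regression template is printed under the secondary analysis, but the only section that calls for a logistic model is 2.5.4, as support for the primary endpoint. Section 4 does not list the change.

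**Step 3: does the sentence in SAP 2.7 on prior information explain it?** Section 2.5.2 uses similar wording for a purely descriptive summary, so the sentence may signal that secondary analyses are non-Bayesian. It neither identifies a protocol change nor gives a reason. At Week 12 the protocol planned no historical prior, so leaving out historical data removes nothing there. At Week 52, dropping Beta(10, 43) does not require dropping the comparison: SAP 2.5.4 itself plans Beta(0.5, 0.5) in both arms for the primary endpoint.

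**Step 4: illustrate the size.** Inputs: n = 25 per arm (Protocol 5.2); priors from Protocol 9.4.2 and 9.5.1; all responder counts y1 (secukinumab) and y2 (placebo) are assumed. Posteriors are Beta(a + y, b + n - y):

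- Secukinumab: Beta(0.5 + y1, 25.5 - y1).
- Placebo without historical data: Beta(0.5 + y2, 25.5 - y2).
- Placebo with Beta(10, 43): Beta(10 + y2, 68 - y2), since 43 + 25 = 68.

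RD = p1 - p2 and OR = [p1/(1 - p1)] / [p2/(1 - p2)], from 4 million draws per arm. Results are medians with 95% credibility intervals.

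Week 12, Beta(0.5, 0.5) in both arms, the same 20-point gap each time:

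| Assumed counts | SAP shows | Posteriors | RD | OR |
|---|---|---|---|---|
| 20 vs 15 | 80% vs 60% | Beta(20.5, 5.5), Beta(15.5, 10.5) | 0.19 (-0.05 to 0.43) | 2.6 (0.8 to 9.8) |
| 22 vs 17 | 88% vs 68% | Beta(22.5, 3.5), Beta(17.5, 8.5) | 0.19 (-0.03 to 0.41) | 3.4 (0.9 to 16) |
| 24 vs 19 | 96% vs 76% | Beta(24.5, 1.5), Beta(19.5, 6.5) | 0.19 (0.01 to 0.39) | 6.6 (1.1 to 84) |

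A check without any prior on the first row gives RD 0.20 with a Newcombe 95% confidence interval of -0.053 to 0.422, close to the Bayesian result.

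Week 52, both candidate placebo priors:

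| Assumed counts | SAP shows | Placebo prior | RD | OR | P(OR > 1) |
|---|---|---|---|---|---|
| 12 vs 5 | 48% vs 20% | Beta(0.5, 0.5) | 0.27 (0.02 to 0.51) | 3.6 (1.1 to 13.5) | 0.98 |
| 12 vs 5 | 48% vs 20% | Beta(10, 43) | 0.29 (0.08 to 0.50) | 4.0 (1.5 to 10.6) | 0.997 |
| 10 vs 5 | 40% vs 20% | Beta(0.5, 0.5) | 0.19 (-0.05 to 0.43) | 2.6 (0.8 to 9.8) | 0.94 |
| 10 vs 5 | 40% vs 20% | Beta(10, 43) | 0.21 (0.01 to 0.42) | 2.9 (1.1 to 7.7) | 0.98 |

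The percentages alone convey none of this uncertainty. With 10 versus 5 responders, the choice of placebo prior alone decides whether the RD interval includes zero.

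**The case against.** The strongest reply is that the SAP may depart from the protocol before unmasking. On that view, a descriptive plan for non-key secondary endpoints is legitimate, it is stated openly in 2.7 and 2.7.2, and only a label and a reason are missing. Part of this stands: the method is not concealed, and an entry in Section 4 would cure the missing declaration. It would still leave an objective framed as efficacy versus placebo without an estimate, although the code to produce one is already in the SAP.

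Other points have some weight.

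- **Interim SAPs.** They were not supplied and may contain these comparisons. That limits what can be said about interim use. It does not change what this SAP plans for the study report.
- **The logistic template in 5.5.** It carries covariates that 2.5.4 does not mention, so it might be a remnant of an intended secondary model. No secondary section calls for it.
- **The illustrations.** They use chosen counts, and no decision rule depends on whether an interval excludes zero. That is correct; they show lost precision, not a wrong decision.
- **Non-responder rules.** SAP 2.7.3 counts stopping study treatment, whereas Protocol 9.5.1 counts leaving the study. This is a separate discrepancy. It does not prevent the comparison from being run on the SAP's own responder counts.

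**Conclusion.** The concern holds. The SAP drops two between-arm comparisons that the protocol specifies, does not identify this as a departure, and gives no reason. As written, it plans no effect estimate or interval for either endpoint. At 25 per arm the missing RD intervals would be about 0.4 to 0.5 wide under the assumed counts (for example 0.43 + 0.05 = 0.48 for 20 versus 15).

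The consequence is bounded. SAP 2.6 names no key secondary objectives, the go criteria in SAP 2.5.2 use only the primary-endpoint RD, and the primary analysis is untouched. The textual conclusion rests on the SAP as supplied; the numerical illustrations rest on assumed counts. This should be corrected, but it does not threaten the trial's main result.

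**What to change.** 1. In SAP 2.7.2, restore the posterior median and 95% credibility interval of OR, RD and RR for both endpoints, and P(OR > 1) at Week 52, using the sampling code in 5.5. Keep the per-arm summaries alongside.
2. At Week 12, use Beta(0.5, 0.5) in both arms, as Protocol 9.5.1 requires.
3. At Week 52, state whether the historical placebo prior carries over. Protocol 9.4.2 says that response rate "will be used as the prior distribution for the placebo response rate for the primary endpoint in this study", so its use at Week 52 is not self-evident. If it does not carry over, use Beta(0.5, 0.5) in both arms and declare this with its reason in Section 4. Decide before the study team is unblinded. Because Protocol 5.4 lets a selected sponsor team see interim results, the choice should rest with people who have not seen them.
4. Amend the sentence on prior information in SAP 2.7 so that it does not contradict these analyses.

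**Cost.** Two extra tables from existing code, one edited sentence and possibly one Section 4 entry. The primary analysis and go criteria do not change. The drawback is two more contrasts with wide intervals and no multiplicity adjustment, so they should be labelled as estimates only.
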